Interventions and Duration	
Subjects will be screened in the 28 days prior to inpatient admission. Subjects will be admitted to the inpatient clinic on the day prior to dosing (Day -1) and will remain in the unit until discharge on Day 3. A follow-up visit will be done on Day 7. A single dose of study drug or placebo will be administered on Day 1.
 
40 healthy adult subjects will be assigned to one of 5 dose cohorts (8 subjects each). The starting dose (10 mg) cohort 1 will include male and female subjects; cohorts 2 – 5 will include only female subjects. Within each cohort, 8 subjects will be randomized to receive MW151 or placebo in the ratio 6:2. According to the dosing scheme each subject will receive a single dose of MW151 or placebo under fasted conditions.
 
1. Starting dose: Dose1 (10 mg)2. Dose2 (20 mg)3. Dose3 (40 mg)4. Dose4 (80 mg)5. Dose5 (160 mg) 
As a safety consideration two sentinel subjects in each cohort will be administered MW151 or placebo in a 1:1 ratio.

-----------------------------------	--

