4.4.5 Randomization/Treatment Assignment

An independent statistician will be responsible for generating the randomization scheme.

The randomization scheme for this study will assign subjects to treatment or placebo in sentinel groups of 2 subjects with a 1:1 ratio (1 drug: 1 placebo), followed by groups of 6 individuals with a 5:1 ratio (5 drug: 1 placebo), so that in each dosing cohort 6 subjects will receive MW151 and 2 subjects will receive placebo (see [Table 3](#)). Randomization numbers will start at 001.

Table 3: Randomization Scheme

Groups	Subjects per Group (MW151: Placebo)	Dose Level	Subjects per Dose Level (MW151: Placebo)
1	2 (1:1)	10 mg MW151 or placebo	8 (6:2)
2	6 (5:1)		
3	2 (1:1)	20 mg MW151 or placebo	8 (6:2)
4	6 (5:1)		
5	2 (1:1)	40 mg MW151 or placebo	8 (6:2)
6	6 (5:1)		
7	2 (1:1)	80 mg MW151 or placebo	8 (6:2)
8	6 (5:1)		
9	2 (1:1)	160 mg MW151 or placebo	8 (6:2)
10	6 (5:1)		

After a subject is confirmed eligible for dosing on the afternoon/evening of Day -1 or morning of Day 1, the study staff will allocate the next available randomization number to the subject, starting at the lowest number and continuing in a consecutive manner.

Once a randomization number has been assigned, it cannot be re-assigned to any other subject. To respect treatment allocation and the overall study design, replacement subjects will receive the same treatment assignment as the original subject who is being replaced and their randomization number will be the initial randomization number plus 100 (i.e. a subject replacing '009' will have the number '109').

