The present first-in-human study will provide safety and pharmacokinetic (PK) information on single ascending doses (SAD) of MW151 to support decisions for continued clinical development. This study will assess the safety, tolerability, and PK profile of escalating single doses of MW151 in healthy adult participants. The trial design will be a double-blind, placebo-controlled, SAD study of MW151 in healthy volunteers. Five dosing cohorts are initially planned. All subjects and the study personnel responsible for assessing adverse events (AEs) will be blinded. This statistical analysis plan (SAP) provides a more technical and detailed elaboration of the statistical analyses of safety and tolerability data as outlined in the protocol.

In the study design, 40 healthy male and female volunteers, ages 18-50 years, will be dosed in 1 of 5 dosing cohorts of 8 subjects each. Subjects will be admitted to the inpatient clinic on the day prior to dosing (Day -1) and will remain in the unit until discharge on Day 3. A follow-up visit will be done on Day 7.

A single dose of study drug or placebo will be administered as an oral capsule(s) on Day 1. Five different doses of MW151 will be evaluated in 5 sequential cohorts. Dosing will start at the lowest dose, then escalate in the 2nd cohort, then escalate sequentially in the 3rd, 4th, and 5th cohorts.

Cohort 1: Dose1: MW151/101 10 mg (or matched placebo), 1 x 10 mg capsule administered orally.

Cohort 2: Dose2: MW151/101 20 mg (or matched placebo), 1 x 20 mg capsule administered orally.

Cohort 3: Dose3: MW151/101 40 mg (or matched placebo), 2 x 20 mg capsule administered orally.

Cohort 4: Dose4: MW151/101 80 mg (or matched placebo), 1 x 80 mg capsule administered orally.

Cohort 5: Dose5: MW151/101 160 mg (or matched placebo), 2 x 80 mg capsule administered orally.

As a safety consideration, two sentinel subjects in each cohort will be administered MW151 or placebo in a 1:1 ratio. Dosing of the remaining subjects in a cohort may proceed after review of sentinel subject safety and tolerability data collected during the first 24 hours of dosing and

determination that no stopping rules are met. The remaining 6 subjects will be randomized in a 5:1 ratio. The remaining subjects in each cohort will be dosed sequentially, not simultaneously.

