7.0 STATISTICAL ISSUES

7.1 GENERAL ANALYSIS CONVENTIONS

General statistical approaches are presented below.

All subjects in the Safety Population will be included in the safety analysis grouped by cohort and treatment group. Statistical analysis of safety data will be descriptive.

Baseline is defined as the last assessment prior to dosing of study medication.

For continuous variables, summaries will include sample size, mean, median, standard deviation, minimum, and maximum. For categorical variables, the summaries will include frequencies and corresponding percentages. No inferential hypothesis testing will be performed. Repeat or unscheduled results will not be included in the summaries, but will be listed. Data from placebo subjects will be pooled for final presentations.

Missing data results will not be imputed. Data summaries and analyses (e.g. means) will be calculated using all available data. If the start day for an AE is missing, day of study drug administration will be used and AE will be considered treatment emergent. Neither month nor year will be imputed for AE.

Statistical analyses will be performed in SAS, Version 9.4 or newer.

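### Sentinels are half of the placebo subjects but one-sixth of the MW151 subjects, and no planned safety summary separates or flags them

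*Combined protocol and SAP*

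**What the plan says.** Protocol 4.4.5 and its Table 3 assign subjects in "sentinel groups of 2 subjects with a 1:1 ratio (1 drug: 1 placebo), followed by groups of 6 individuals with a 5:1 ratio", so that "in each dosing cohort 6 subjects will receive MW151 and 2 subjects will receive placebo". For each eligible subject "the study staff will allocate the next available randomization number to the subject", in consecutive order from the lowest. Sentinels go first: under SAP 2.0, "Dosing of the remaining subjects in a cohort may proceed after review of sentinel subject safety and tolerability data" from the first 24 hours.

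SAP 7.1 groups the safety analysis by cohort and treatment group, keeps it descriptive without hypothesis tests, and states: "Data from placebo subjects will be pooled for final presentations". Protocol 9.1 pools placebo in the same way. SAP 10.1 to 10.4 tabulate adverse events, laboratory values, vital signs and ECGs by treatment group with dose or cohort. None of these sections uses the sentinel and non-sentinel groups.

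**The concern.** Treatment is randomised within each group of Table 3, but the chance of active drug is 1 in 2 for a sentinel and 5 in 6 for everyone else. A table that ignores the group therefore sets a placebo column that is half sentinels beside an MW151 column that is one-sixth sentinels. The columns are not like for like unless sentinels and others would have the same results.

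They might not. Consecutive numbering implies that sentinels are the first eligible subjects in a cohort rather than a random pair, and they are the first to receive each new dose level. Adverse events are elicited by an open question about how the subject feels (protocol section 7), which could be answered differently in that setting. Safety and tolerability are the primary objective, and readers will judge them largely by looking across these columns. A difference between sentinels and others would show up there as a drug-placebo difference even if the drug did nothing.

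**Working it through.** **Inputs** (protocol 4.4.5, Table 3): sentinels 1 MW151 and 1 placebo per cohort; remainder 5 MW151 and 1 placebo; five cohorts.

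**1. The plan's own figure.** Per cohort (1+5):(1+1) = 6:2, which is 8. Over five cohorts 30:10, which is 40. Both match the protocol.

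**2. Sentinel share by column.**

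| Comparison | MW151 | Placebo | Difference |
|---|---|---|---|
| All MW151 v pooled placebo | 5/30 = 1/6 | 5/10 = 1/2 | -1/3 |
| One dose v pooled placebo | 1/6 | 5/10 = 1/2 | -1/3 |
| Within one cohort | 1/6 | 1/2 | -1/3 |

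The last row shows that pooling across cohorts is not the source.

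**3. Effect on the contrast.** Let D be the sentinel minus non-sentinel difference in a mean or proportion, equal in both arms, with no drug effect. Each column equals the non-sentinel value plus (sentinel share x D), so MW151 minus placebo = (1/6 - 1/2) x D = -D/3. A simulation of 50,000 trials gave -0.334 D without stratification and -0.001 D with it. If the effect differs by arm, the shift is D(MW151)/6 - D(placebo)/2.

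**4. Illustration (D is assumed).** With adverse event rates of 40% in sentinels and 20% in others:
- MW151: (5 x 0.40 + 25 x 0.20)/30 = 23.3%
- Placebo: (5 x 0.40 + 5 x 0.20)/10 = 30.0%
- Difference: -6.7 points with no drug effect

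For D of 10, 20 and 30 points the shift is -3.3, -6.7 and -10.0 points. A negative D reverses the sign.

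**5. Sensitivity to losing a subject.** Without one sentinel placebo subject: 5/30 - 4/9 = -5/18. Without one non-sentinel placebo subject: 5/30 - 5/9 = -7/18.

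**6. Price of a stratified overall difference.** Mantel-Haenszel weights are 5x5/10 = 2.5 and 25x5/30 = 4.17, total 6.67, against 30x10/40 = 7.5 unstratified. The variance ratio is 7.5/6.67 = 1.125, so the standard error (SE) is about 6% larger.

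Mean squared error, with a non-sentinel rate of 20% (r = 0.16) and s = p(1-p) for sentinels:
- Pooled: (5s+25r)/900 + (5s+5r)/100 + (D/3)²
- Stratified: 0.375² x 2s/5 + 0.625² x (r/25 + r/5)

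| D | s | Pooled | Stratified |
|---|---|---|---|
| 10 points | 0.21 | 0.0252 | 0.0268 |
| 20 points | 0.24 | 0.0302 | 0.0285 |

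Pooling does slightly better at 10 points and stratifying slightly better at 20.

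**The case against.** The strongest reply is that there is no planned contrast to bias. The SAP specifies no difference, model or test. The halting and escalation criteria in protocol 8.1 count events or subjects, and reviews between cohorts are blinded unless a safety concern arises. This stands: no error rate and no written decision rule is affected. What remains is how the side-by-side columns are read.

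Next, D is hypothetical. Both groups share eligibility criteria, unit and assessment schedule, and the non-sentinels are also dosed one after another, which narrows the contrast. This stands too, and it limits what can be said about size and direction.

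Third, the shift is small against the noise. In the illustration it is 6.7 points, while the SE of the pooled difference is √[(5x0.24+25x0.16)/900 + (5x0.24+5x0.16)/100], about 16 points. As the working shows, a weighted estimator can do worse than pooling when D is modest. This rules out replacing the planned tables with weighted estimates. It does not argue against showing the groups.

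Finally, everything is listed, and sentinel status should be recoverable from the randomisation numbers. That is true, but a reader would have to rebuild it from listings that carry no such flag.

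A reader might also infer that blinded raters will call more events drug-related on MW151 because they know the odds. The documents do not support that: protocol 7.2 and 7.3 base relatedness on timing, alternative explanations and plausible mechanism.

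**Conclusion.** The imbalance is exact: 1/2 against 1/6, overall, for each dose against pooled placebo, and within each cohort. The planned summaries ignore it. The consequence is conditional: a shift of -D/3 in the apparent MW151-minus-placebo difference, for means and proportions only, assuming an additive sentinel effect equal in both arms and no lost subjects. Medians, minima and maxima do not follow this formula.

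Three stronger readings are tempting and go too far:
- That pooling placebo causes the problem. It does not, because the gap is the same inside one cohort.
- That MW151 will look safer than it is. That requires D to be positive, and the documents say nothing about its sign.
- That every comparison is biased by a third of a real effect. Nothing in the documents shows that a sentinel effect exists.

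The point is worth acting on because the display can follow the trial's own randomisation groups at almost no cost, and the reader could then see whether sentinels differ.

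**What to change.** In SAP 7.1 and 10.1 to 10.4:
- Define sentinel/non-sentinel (the randomisation group of protocol Table 3) as a classification variable, derived from the randomisation number.
- Keep the planned pooled tables. Beside them, add adverse event and clinically notable value summaries by group for all MW151 against placebo: 5 v 5 sentinels and 25 v 5 others.
- Flag sentinel status in the listings.
- Optionally, give a Mantel-Haenszel-weighted overall difference as a supplementary descriptive figure, accepting an SE about 6% larger.

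I would not reweight placebo to a one-sixth sentinel share for each dose. With weights of 1/30 per sentinel and 1/6 per non-sentinel, the variance is 1/6 + 5/30² + 5/6² = 0.311 σ² against 1/6 + 1/10 = 0.267 σ², so the SE is about 8% larger with a single sentinel per dose on MW151.

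The cost is SAP wording and a few extra tables, with no new data or subjects. The drawback is small strata: counts in the 5 v 5 table can only be read descriptively.

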8.0 EXTENT OF EXPOSURE**8.1 STUDY MEDICATION**

Exposure to study medication for the Safety Population will be summarized in terms of the amount of dose administered (in mg) for each dose cohort and treatment group. Concomitant medications will be listed. Any instance of a subject receiving a dose other than the assigned dose will be listed. Descriptive statistics will be presented by treatment group.

9.0

PHARMACOKINETIC ANALYSIS

The PK analysis is outside the scope of this SAP and is described in a separate PK statistical analysis plan.

10.0 SAFETY ANALYSES

The safety analysis will be performed using the Safety Population. Safety and tolerability will be assessed on the basis of physical examination, neurological examination, vital signs, clinical laboratory values, ECG readings, and adverse event (AE) reports.

Statistical analysis of safety data will be descriptive.

10.1 ADVERSE EVENT ASSESSMENTS

Adverse events (AEs) will be coded using the Medical Dictionary for Regulatory Activities (MedDRA) v21.0 – 5 Level or newer. AEs will be listed and summarized by treatment group and dose level. Where applicable, AEs may also be listed by severity, seriousness, relationship to study treatment and by system organ class and preferred term.

A treatment-emergent AE (TEAE) is an AE, regardless of relationship to study drug, which occurs during or after the first dose of study treatment. TEAE will be summarized by MedDRA System Organ Class and Preferred Term.

10.2 CLINICAL LABORATORY TESTING

Summary statistics of observed and change from baseline data will be presented for each treatment group and dose where applicable. Shift tables summarizing the numbers of subjects shifting from normal pre-dose values to abnormal post-dose values will also be presented where applicable. Listings for all safety laboratory assessments will be presented.

Lab tests included will be all in the hematology and coagulation panel, biochemistry panel, and urinalysis panel (as needed lab tests: RBC, WBC, hyaline casts, cellular casts, and granular casts will only be presented as listings).

10.3 VITAL SIGNS

Vital signs (supine systolic and diastolic blood pressure, orthostatic change in systolic and diastolic blood pressure, supine heart rate/pulse, body temperature) and changes from baseline at each time point will be presented by cohort and treatment group. Listings for all vital signs and orthostatic change will be presented.

Clinically notable vital signs will be listed and summarized by treatment group and dose. Criteria for Clinically Notable vital sign abnormalities are indicated in Table 2 below.

Table 2: Criteria for Clinically Notable Vital Sign Abnormalities

Parameter	High Threshold	Low Threshold
Systolic BP (supine)	> 30 mmHg increase from baseline	> 30 mmHg decrease from baseline
Diastolic BP (supine)	> 20 mmHg increase from baseline	> 30 mmHg decrease from baseline
Heart Rate (supine)	> 120 bpm and an increase in HR of ≥ 15 bpm from baseline	< 40 bpm and a decrease in HR of ≥ 15 bpm from baseline
Body Temperature	> 39.0°C ($> 102.2^{\circ}\text{F}$)	< 35.0°C ($< 95.0^{\circ}\text{F}$)

10.4 ELECTROCARDIOGRAM MONITORING

ECG parameters (e.g. Ventricular Heart Rate, PR interval, QRS interval, QTc interval, QTcB, QTcF interval, and RR interval) and changes from baseline at each assessment time point will be presented by cohort and treatment group. Listings for ECG parameters will also be presented.

Clinically notable ECGs will be listed and summarized by treatment group and dose. Criteria for Clinically notable ECG abnormalities are indicated in Table 3 below:

Table 3: Criteria for Clinically Notable ECG Abnormalities

Parameter	High Threshold	Low Threshold
PR interval	PR ≥ 220 ms	PR ≤ 120 ms
QRS duration	QRS duration ≥ 120 ms and an increase of ≥ 20 ms from baseline	-
QT interval	QT interval > 500 ms	-
QTcF interval	Men: QTcF interval ≥ 450 ms and an increase of ≥ 60 ms from baseline OR QTcF interval > 500 ms Women: QTcF interval ≥ 470 ms and an increase of ≥ 60 ms from baseline OR QTcF interval > 500 ms	-

10.5 PHYSICAL EXAMINATIONS

Descriptive statistics for weight at baseline and changes from baseline at each assessment time point will be presented by cohort and treatment group. A listing of physical examination data for all subjects will be provided.

10.6 NEUROLOGICAL EXAMINATIONS

Neurological examinations include mental status, cranial nerves 2-12, motor system and coordination, reflexes, and sensory system. Shift tables summarizing the numbers of subjects shifting from normal pre-dose values to abnormal post-dose values will be created. A listing of abnormal neurological examination data for all subjects will be provided.

11.0 DETERMINATION OF SAMPLE SIZE

This trial is designed to investigate the safety, tolerability, and PK properties of the drug MW151 in a dose escalation Phase Ia study. The number of subjects is based upon the need to gain this knowledge in healthy individuals using as few subjects as possible. Since this is the first study of MW151 in humans, there is no prior experience upon which to base estimates of variability for the PK responses to SAD treatment with MW151. No power analysis is conducted but the cohort size is based on accepted standards in similar Phase I studies: 8 subjects per dose with 6 randomly assigned to active drug while the remaining 2 subjects receive placebo. Eight subjects per cohort was deemed sufficient for obtaining an adequate preliminary description of the responses of interest.

Appendix A

Table 1. Schedule of Activities

Day/Procedures	Screening (¹)	-1 Admission	1	2	3 Discharge (²)	7 FU visit
Informed consent	X					
Inclusion/Exclusion Review	X	X				
Demographics	X					
Medical History	X	X				X
Columbia Suicide Severity Rating Scale	X					
Physical Examination ⁽³⁾	X	X		X		X
Infection Screen ⁽⁴⁾		X				
Body Temperature ⁽⁵⁾	X	X	X	X	X	X
Neurological Examination ⁽⁶⁾		X		X		
Safety Laboratory Tests ⁽⁷⁾	X	X		X		X
Drug Screen (urine)	X	X				
Alcohol Screen (breathalyzer)	X	X				
Hepatitis B & C/ HIV Screen	X					
TB test (blood test)	X					
Pregnancy Test (serum at Screening/urine on D-1)	X	X				
12-lead ECG ⁽⁸⁾	X	X	X	X	X	X
Vital signs (BP/HR) ⁽⁹⁾	X	X	X	X	X	X
PK blood sampling ⁽¹⁰⁾			X	X		
Admit to Unit/Randomization ⁽¹¹⁾		X				
Dosing ⁽¹²⁾			X			
Adverse Event Assessment			X	X	X	X
Concomitant Medication Review	X	X	X	X	X	X
Discharge from Unit					X	

Footnotes to Schedule of Activities

(1) Screening will occur within 28 days of dosing.

(2) Subjects who discontinue from the study should undergo all Early Termination assessments as per the Day 3 visit.

(3) Weight will be measured during all physical examinations and height will be measured at Screening only. Physical examination will include general appearance; head, eyes, ears, nose, throat (HEENT); cardiovascular; lung; abdominal; musculoskeletal; and skin.

(4) On Day -1, subjects will be screened for the presence of infection as part of physical examination, body temperature, recent/current antibiotic use, recent surgery, evidence of dental abscess, unhealed skin lesions etc. On Day 1 before dosing, subjects will be screened for emergence of acute illness.

(5) Body temperature will be measured at the following time-points:

- Screening
- Day -1
- Day 1 before dosing and again at 12h post-dose
- Day 2 – Day 3 approximately 24h and 48h, respectively, after dosing
- Day 7

(6) Neurological examination will include mental status evaluation, cranial nerves 2-12 testing, motor system and coordination testing, reflex evaluation and sensory system evaluation. The neurological examination should be conducted at the same time as the physical examination when both are scheduled on the same study day.

- Day -1
- Day 2

(7) Safety laboratory samples (Hematology/Coagulation/Biochemistry/Urinalysis) will be taken after the subject has fasted for a minimum of 10 hours as follows:

- Screening (all except creatine kinase, amylase, lipase, cholesterol, HDL/LDL/triglycerides)
- Day -1
- Day 2
- Day 7

(8) A 12-lead ECG will be performed (after lying quietly for 5 minutes). Triplicate tracings (3x) will be taken at Day -1 only and will serve as the Baseline (pre-dose measurement). ECGs will be performed at the following time points.

- Screening
- Day -1
- Day 1: approximately 1h, 2h, 4h, and 12h post-dose
- Day 2: approximately 24h post-dose
- Day 3
- Day 7

Subjects will be monitored on telemetry from approximately 30 min prior to dosing through the 4 hour post-dose ECG.

(9) Vital signs will include BP and HR. At each time point where vital signs are measured, heart rate and blood pressure will first be checked in the supine position and then in the standing position with at least 2 minutes between the supine and standing measurements. Vitals will be performed at the following time-points:

- Screening
- Day -1
- Day 1: Pre-dose and at 1h, 2h, 4h, and 12h post-dose
- Day 2: approximately 24h and 36h post-dose
- Day 3

- Day 7

(10) PK samples will be taken at the following time-points, anchored to the start of dosing.

- Day 1: Pre-dose, and 0.25h, 0.5h, 1h, 2h, 4h, 8h, 12h post-dose
- Day 2: 24h and 36h post-dose

(11) Randomization is expected to occur on D-1, but if there are delays in receiving prequalification safety labs randomization may occur on D1 prior to dosing.

(12) Dosing will be by oral capsule administration, on day 1.

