Cranial Nerves 2-12: Test visual fields, visual acuity, pupillary reflexes, eye movements, fundoscopy, facial strength (including facial expression and mastication), hearing to finger rub, tongue, palate and head rotation movements, check for dysarthria and shoulder elevation.

Motor System and Coordination: Test strength in upper and lower limbs bilaterally, pronator drift, finger tapping, rapid pronation and supination movements, finger-nose, heel shin, tandem gait, walking on heels.

Reflexes: Test biceps, triceps, knee, ankle and plantar responses (Babinski's reflex).

Sensory System: Test light touch, vibration, Romberg test.

Safety Exclusions: Safety laboratory tests performed as part of Screening and Day -1 assessments **may not be repeated** if any quantitative exclusion criteria are met.

Pre-dose vital signs (Screening, Day -1, Day 1 pre-dose) may be repeated once at each visit to confirm exclusionary findings. In cases where the initial assessment is exclusionary and the repeat assessment is not, the Investigator must evaluate both sets of data and determine whether or not the subject may continue.

Pre-dose ECGs (Screening, Day -1 pre-dose) **may not be repeated** if any quantitative exclusion criteria (QTcF) are met. Other abnormal ECGs may be repeated once at each visit to confirm non-quantitative exclusionary findings. In cases where the initial assessment is exclusionary and the repeat assessment is not, the Investigator must evaluate both sets of data and determine whether or not the subject may continue.

Subjects must not be randomized if there are any clinically significant pre-dose findings on vital signs, ECGs, safety laboratory tests, physical examinations and/or neurological examinations.

Electrocardiogram: A standard 12-lead ECG will be collected at required time points (after lying quietly for 5 minutes). ECG parameters including HR, PR, QT, QTcB, QTcF, QRS, and RR intervals will be collected.

At Day -1, pre-dose triplicate ECG tracings will be obtained and will serve as the Baseline. At all other time points, a single ECG tracing will be obtained.

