9 STATISTICAL CONSIDERATIONS

9.1 General Design Issues

Detailed statistical analysis plans will be created for the study and signed off in advance of database lock. One plan will be created for the analysis of PK data and a separate plan will be created for the analysis and presentation of all other study data. General statistical approaches are presented below. Baseline is defined as the last evaluation before dosing.

Safety Analysis: All subjects who receive any study treatment will be included in the safety analysis grouped by treatment received. Statistical analysis of safety data will be descriptive.

For continuous variables, summaries will include sample size, mean, standard deviation, minimum, and maximum. For categorical variables, the summaries will include frequencies and corresponding percentages. No inferential hypothesis testing will be performed on the safety variables. Repeat or unscheduled results will not be included in the summaries, but will be listed. Data from placebo subjects will be pooled for final presentations. Confidence intervals (90%, 95%) may be used in safety summaries.

Adverse Events: AEs will be coded using the Medical Dictionary for Regulatory Activities (MedDRA). AEs will be listed and summarized by treatment group and dose level. Where applicable, AEs may also be summarized by severity, seriousness, relationship to study treatment and by system organ class and preferred term. The number and percentage of subjects who experience events will be shown in the summaries. Listings for all AEs will be presented.

A treatment-emergent AE is an AE, regardless of relationship to study drug that occurs during or after the first dose of study treatment.

Laboratory Assessments: Summary statistics of observed and change from baseline data will be presented for each treatment group and dose level where applicable. Summary statistics will include number of subjects, mean, standard deviation, minimum, and maximum. Shift tables summarizing the numbers of subjects shifting from normal pre-dose values to abnormal post- dose values will also be presented where applicable. Listings for all laboratory assessments will be presented.

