Vital Signs (BP, HR, Body Temperature): Summary statistics for BP and HR and change from baseline (predose) summaries will be presented for each treatment group and dose level where applicable. Summary statistics will include number of subjects, mean, standard deviation, minimum, and maximum. Listings for all vital signs will be presented.

Post-dose clinically notable vital signs will be listed and summarized by treatment and dose. Notable abnormalities are indicated in **Table 5** below:

Table 5: Criteria for Clinically Notable Vital Sign Abnormalities

Parameter	High Threshold	Low Threshold
Systolic BP (supine)	> 30 mmHg increase from baseline	> 30 mmHg decrease from baseline
Diastolic BP (supine)	> 20 mmHg increase from baseline	> 30 mmHg decrease from baseline
Heart Rate	> 120 bpm and an increase in HR of ≥ 15 bpm from baseline	< 40 bpm and a decrease in HR of ≥ 15 bpm from baseline
Body Temperature	> 39.0°C ($> 102.2^{\circ}\text{F}$)	< 35.0°C ($< 95.0^{\circ}\text{F}$)

12-Lead ECG: ECG results from the central reader will be used in the analysis. Shift tables summarizing the numbers of subjects shifting from normal pre-dose values to abnormal post-dose values will also be presented. Numeric ECG data will be summarized by treatment group and dose level and mean summary tables, including change from baseline will be presented.

The ECG results will be listed by treatment group and dose level.

Post-dose clinically notable ECGs will be listed and summarized by treatment and dose. Notable abnormalities are indicated in [Table 6](#) below:

Table 6: Criteria for Clinically Notable ECG Abnormalities

Parameter	High Threshold	Low Threshold
PR interval	PR ≥ 220 ms	PR ≤ 120 ms
QRS duration	QRS duration ≥ 120 ms and an increase of ≥ 20 ms from baseline	-
QT interval	QT interval > 500 ms	-
QTcF interval	Men: QTcF interval ≥ 450 ms and an increase of ≥ 60 ms from baseline OR QTcF interval > 500 ms Women: QTcF interval ≥ 470 ms and an increase of ≥ 60 ms from baseline OR QTcF interval > 500 ms	-

Pharmacokinetic Analysis: The plasma concentrations of MW151 will be determined, and used to estimate appropriate PK parameters including C_{max} , T_{max} , AUC, $T_{1/2}$ and K_{el} by non- compartmental analysis. The PK analysis population will include all subjects who received the active study drug and who have sufficient MW151 plasma concentrations to calculate at least 1 PK parameter.

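### Does the plan need a written rule for turning the Day -1 ECG triplicate into one baseline, and a correction because SAP 10.4 omits the ECG shift table?

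*Combined protocol and SAP*

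**What the plan says.** The ECG-specific rule appears in three places. Footnote 8 to the schedule, in protocol 6.1 and again in SAP Appendix A, reads: "Triplicate tracings (3x) will be taken at Day -1 only and will serve as the Baseline (pre-dose measurement". Protocol 6.2.1 agrees: "At Day -1, pre-dose triplicate ECG tracings will be obtained and will serve as the Baseline". It adds that every other time point has a single tracing.

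The general rules are consistent with this. Protocol 9.1 has "Baseline is defined as the last evaluation before dosing" and SAP 7.1 has "Baseline is defined as the last assessment prior to dosing of study medication". SAP 7.1 also states: "Repeat or unscheduled results will not be included in the summaries, but will be listed". Protocol 6.2.1 allows a limited pre-dose repeat: "Other abnormal ECGs may be repeated once at each visit to confirm non-quantitative exclusionary findings".

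On outputs, protocol 9.1 says under 12-Lead ECG: "Shift tables summarizing the numbers of subjects shifting from normal pre-dose values to abnormal post-dose values will also be presented". SAP 10.4 plans parameter values and changes from baseline at each time point, a table of clinically notable ECGs, and listings ("Listings for ECG parameters will also be presented"). It does not mention a shift table.

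**The concern.** SAP 10.4 needs one baseline number per subject and parameter. It feeds every change from baseline and the increase part of two notable-ECG criteria: at least 20 ms for QRS and at least 60 ms for QTcF. Three tracings are three numbers, and no sentence reduces them to one. A subject with a repeat ECG on Day -1 seems to add a conflict: the last-assessment rule could point to the repeat, while the ECG-specific rule points to the triplicate.

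The missing shift table looks like a silent loss. The SAP keeps a laboratory shift table (10.2) and adds a neurological one (10.6), so an absent ECG table could be read as a decision to drop it. QT prolongation is a named nonclinical finding (protocol 2.3.1 and 5.1) and safety is the primary objective, so ECG outputs deserve care. The notable-QTcF criterion is also a joint one. A woman who goes from 400 to 469 ms rises by 69 ms without meeting it, and with full enrolment at least 4 × 8 = 32 of the 40 subjects are women.

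**Working it through.** The plan states no figure to reproduce here. The check asks how far the unstated choice can move the results, then compares the two output lists.

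**Which session.** Day 1 ECGs are scheduled at 1, 2, 4 and 12 h after dosing, with none before it. The last pre-dose ECG session is therefore Day -1, and the general and specific rules select the same session. Only the reduction of the three tracings is open.

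**Effect on the baseline number.** Let s be the SD of one tracing within a subject. The documents give no value, so I assume 4 to 10 ms for QTcF and 2 to 5 ms for QRS. For three independent normal tracings:

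- SD(mean − median) = 0.340s. QTcF: 0.340 × 4 = 1.4 ms to 0.340 × 10 = 3.4 ms. QRS: 0.7 to 1.7 ms.
- SD(mean − last tracing) = √(2/3) s = 0.816s. QTcF: 3.3 to 8.2 ms. QRS: 1.6 to 4.1 ms.

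Mean, median and last tracing have the same expectation, so none of them biases a mean change from baseline. The SD of a change (one post-dose tracing minus baseline) is √(1 + 1/3) s = 1.155s with the mean and √2 s = 1.414s with one tracing. Since 1.155/1.414 = 0.816, averaging lowers it by about 18%.

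**Effect on the flags.** The increase part of the QTcF criterion decides only when baseline + 60 lies between the absolute limit and 500 ms:

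- Women: 470 − 60 = 410 to 500 − 60 = 440 ms.
- Men: 450 − 60 = 390 to 440 ms.
- QRS: only above 120 − 20 = 100 ms.

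Outside these ranges an absolute limit decides. Inside them, the choice matters only if the rise is close to the threshold. The table gives the chance that a true QTcF rise of 50 ms reads as 60 ms or more, for the increase part alone (simulation, 1,000,000 draws, assumed s):

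| Baseline used | s = 5 ms | s = 8 ms | s = 10 ms |
|---|---|---|---|
| Mean of three | 4.2% | 13.9% | 19.3% |
| Median of three | 4.8% | 14.9% | 20.3% |
| Last tracing | 7.9% | 18.9% | 23.9% |

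Mean and median differ by 0.6 to 1.0 percentage points. The last tracing differs from the mean by 3.7 to 5.0 points, but using it would set aside two of the three tracings that footnote 8 makes the baseline.

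**Repeat ECG on Day -1.** The repeat serves to confirm an eligibility finding and is barred when the QTcF criterion itself is met. The ECG-specific rule names the triplicate, and SAP 7.1 keeps repeat results out of summaries. Only the generic last-assessment rule could point elsewhere, and a specific rule takes precedence over a generic one.

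**Shift table.** Protocol 9.1 plans it. SAP 10.4 neither lists nor withdraws it. The SAP introduction describes the document as a more detailed account of the protocol's safety analyses, so the protocol's commitment still stands.

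**The 400 to 469 ms example.** The first flagged value for a woman with baseline b, in whole ms, is min(max(470, b + 60), 501). The largest unflagged rise is that value − 1 − b: 89 ms at b = 380, 69 at 400, 59 from 410 to 440, and 55 at 445. These gaps come from the joint criterion, which is the same in both documents. Neither a triplicate rule nor a shift table alters it. If 470 ms were the limit of normal for women, 469 ms would count as normal in a shift table too. SAP 7.1 requires minimum and maximum for continuous variables, and SAP 10.4 presents changes by cohort and treatment group. A rise of 69 ms among six active subjects would therefore be the printed maximum or lie below it, and the listings would show the values.

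**The case for a change.** The strongest case for acting is that baseline conventions should be fixed before anyone sees unblinded data, that one sentence would do it, and that ECG findings matter for this compound. If averaging is meant, why not say so? A programmer working only from SAP 10.4 might also never build the shift table, leaving the study report short of an output that the protocol says will be presented.

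Part of this stands. The reduction rule is unwritten, the two lists of ECG outputs differ, and the protocol does not say what counts as normal or abnormal in the shift table, including when the three tracings disagree. These are details of table specification. Settling them would record a convention that the text already implies and repeat an output that the protocol already requires. It would not change an estimate, a decision rule or the data collected. The rules that could move the baseline systematically, the maximum or minimum of the three (about 0.85s in either direction), have no support in either document.

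**Conclusion.** No change follows. The missing reduction rule is a gap that analysts fill sensibly by averaging. Against the nearest alternative, the median, the effect is an SD of 1.4 to 3.4 ms per subject for QTcF and about 1 percentage point or less in the chance of reading a true 50 ms rise as 60 ms or more. Those figures rest on assumed tracing SDs (4 to 10 ms for the first; 5, 8 and 10 ms for the second) and independent normal errors. The repeat-ECG conflict is settled by the ECG-specific rule together with the exclusion of repeats, and the number of subjects concerned may be zero. The shift table is missing from the SAP's list but not from the plan, because protocol 9.1 still requires it. All these outputs are descriptive, and clinically significant post-dose ECG findings are recorded as adverse events whichever baseline is used. The joint QTcF criterion is a separate feature of the thresholds and does not support this concern.
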